7.7.2. Instructions for Reporting Special Situations

7.7.2.1. Instructions for Reporting Pregnancies

The investigator should report pregnancies in female study subjects that are identified after initiation of study medication and throughout the study, including the post study drug follow-up period, to Gilead PVE the pregnancy report form within 24 hours of becoming aware of the pregnancy.

Refer to Section [7.3](#) and the CRF/eCRF completion guidelines for full instructions on the mechanism of pregnancy reporting.

The pregnancy itself is not considered an AE nor is an induced elective abortion to terminate a pregnancy without medical reasons.

Any premature termination of pregnancy (eg, a spontaneous abortion, an induced therapeutic abortion due to complications or other medical reasons) must be reported within 24 hours as an SAE. The underlying medical reason for this procedure should be recorded as the AE term.

A spontaneous abortion is always considered to be an SAE and will be reported as described in Sections [7.1.1](#) and [7.1.2](#). Furthermore, any SAE occurring as an adverse pregnancy outcome post study must be reported to Gilead PVE.

The subject should receive appropriate monitoring and care until the conclusion of the pregnancy. The outcome should be reported to Gilead using the pregnancy outcome report form. If the end of the pregnancy occurs after the study has been completed, the outcome should be reported directly to Gilead PVE. Gilead PVE contact information is as follows:

Email: **PPD** and Fax: **PPD**

Pregnancies of female partners of male study subjects exposed to study drugs must also be reported and relevant information should be submitted to Gilead PVE using the pregnancy and pregnancy outcome forms within 24 hours. Monitoring of the pregnancy should continue until its conclusion. If the end of the pregnancy occurs after the study has been completed, the outcome should be reported directly to Gilead PVE, fax number **PPD** or email **PPD**

Refer to [Appendix 5](#) for Pregnancy Precautions, Definition for Female of Childbearing Potential, and Contraceptive Requirements.

7.7.2.2. Reporting Other Special Situations

All other special situation reports must be reported on the special situations report form and forwarded to Gilead PVE within 24 hours of the investigator becoming aware of the situation. These reports must consist of situations that involve study IMP and/or Gilead concomitant medications, but do not apply to non-Gilead concomitant medications.

Special situations involving non-Gilead concomitant medications does not need to be reported on the special situations report form; however, for special situations that result in AEs due to a non-Gilead concomitant medication, the AE should be reported on the AE form.

Any inappropriate use of concomitant medications prohibited by this protocol should not be reported as “misuse,” but may be more appropriately documented as a protocol deviation.

Refer to Section [7.3](#) and the CRF/eCRF completion guidelines for full instructions on the mechanism of special situations reporting.

All clinical sequelae in relation to these special situation reports will be reported as AEs or SAEs at the same time using the AE CRF/eCRF and/or the SAE report form. Details of the symptoms and signs, clinical management, and outcome will be reported, when available.

8. STATISTICAL CONSIDERATIONS

Efficacy and safety data collected up to Week 16 will be summarized by treatment group for all subjects. Data from subjects who do not switch treatment will be summarized for the duration of the study by treatment group. Summaries by the combinations of treatment groups may be provided, if applicable.

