1.4.1. Rationale for Endpoint and Timing

Change in proteinuria will be the primary measure of efficacy. Proteinuria has long been used as a surrogate endpoint because it correlates well with kidney function, and it has been implicated in the pathogenesis of chronic kidney disease. In LMN it is associated with thromboembolic events, as well as cardiovascular events. Proteinuria is a standardized outcome measure of lupus nephritis, and an attractive choice because following an intervention, the change in proteinuria is often earlier and larger than the observed change in kidney function. It might be useful therefore in slowly progressive or early stages of disease. A magnitude of 35% or greater reduction in proteinuria was selected based on response rates observed during other trials of lupus nephritis {Borchers 2012}, including LMN {Swan 2011}.

Secondary measures will include additional measures of kidney structure and function (eg, proteinuria and glomerular filtration rate) at various time points, as well as measures of lupus activity. Validated scales will be used for lupus, including the Safety of Estrogens in Lupus Erythematosus National Assessment trial-based SLE Disease Activity Index (SELENA-SLEDAI) and the British Isles Lupus Activity Group (BILAG).

The selection of the 16-week time point is based on prior studies of LMN and lupus nephritis more broadly, as well as the speed of action of filgotinib (approximately 80-90% of total clinical benefit achieved by week 12), as demonstrated in Phase 2b studies of subjects with active RA (protocols GLPG0634-CL-203 and GLPG0634-CL-204). Review of the published information on prior randomized studies in lupus nephritis {Borchers 2012} including LMN {Swan 2011}, demonstrates a range of drug administration duration between 10 weeks for cyclophosphamide and 6 months for azathioprine and mycophenolic acid, supporting the idea that a 16-week primary endpoint is both clinically and ethically appropriate and allows an acceptable time to assess initial response to therapy.

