3.3. Study Treatments

Eligible subjects will be randomized in a 1:1 ratio to receive once daily oral doses of the following study drugs for 16 weeks:

Arm	Study Drugs
Filgotinib (n=16)	Filgotinib 200 mg + PTM GS-9876
GS-9876 (n=16)	GS-9876 30 mg + PTM Filgotinib

PTM = Placebo to match

Randomization will be stratified by prior treatment with cyclophosphamide.

Urinary protein excretion will be determined using 2 methods – two consecutive morning voids as well as a 24-hour urine collection. For the Day 1 assessment, all 3 urine samples will be collected prior to Day 1, with the 24-hour urine collection as close to the Day 1 visit as possible. At Week 16, the primary study endpoint will be assessed by urine protein excretion during a

24-hour urine collection. Two consecutive morning voids prior to the Week 16 visit will be used to determine response for subsequent study treatment. All subjects who achieve a $\geq 35\%$ reduction in urinary protein excretion (using an average of the UPCR from 2 morning voids) from Day 1 will continue to receive their assigned blinded study treatment (filgotinib 200 mg + PTM GS-9876, or GS-9876 30 mg + PTM filgotinib) for an additional 16 weeks. Additional details regarding urine collection procedures will be specified in the Laboratory Manual and Subject Procedures Manual.

Subjects who do not achieve a $\geq 35\%$ reduction in urinary protein excretion from Day 1 to Week 16 will switch study treatment for 16 weeks in a blinded fashion (ie, those on filgotinib will switch to GS-9876 + PTM filgotinib, while those on GS-9876 will switch to filgotinib + PTM GS-9876).

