After 32 weeks of blinded treatment, those who have a $\geq 35\%$ reduction in urinary protein excretion (using an average of the UPCR from 2 morning voids) from Day 1 (for subjects who remained on the randomized study treatment after Week 16) or from Week 16 (for subjects who switched treatment at Week 16) will continue their assigned blinded treatment for an additional 20 weeks in the Extended Blinded Treatment Phase. Subjects that do not achieve a $\geq 35\%$ reduction in urinary protein excretion from Day 1 (for subjects who remained on the randomized study treatment after Week 16) or from Week 16 (for subjects who switched treatment at Week 16) to Week 32 will be allowed to continue whichever treatment led to the greatest reduction in urinary protein excretion (from Day 1 to Week 16 on initial study treatment or from Week 16 to Week 32 on switched treatment), or either study treatment per the Investigator's discretion (eg, differences in tolerability or other non-renal benefits that support overriding the treatment assignment according to reduction in urinary protein excretion) during the Extended Blinded Treatment Phase.

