8.9. Sample Size

The sample size was chosen based on the practical considerations and to ensure that a clinically meaningful reduction in proteinuria from Baseline (Day 1) could be detected in any of the treatment groups, filgotinib or GS-9876. With 16 subjects per treatment group (32 subjects total), there is a 80% power to detect a 35% reduction from Baseline (Day 1) in proteinuria at Week 16 with a standard deviation of 50% and a 2-sided 0.05 significance level.

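### The whole-study efficacy summary of subjects who do not switch is selected on the Week 16 outcome, so it would show a fall in proteinuria even for an inert drug

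*Protocol*

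**What the plan says.** Protocol Section 8 opens with two commitments, which the synopsis repeats under Statistical Methods. The first covers everyone but stops at the primary time point: "Efficacy and safety data collected up to Week 16 will be summarized by treatment group for all subjects". The second runs to the end of the study but covers a subset: "Data from subjects who do not switch treatment will be summarized for the duration of the study by treatment group". Summaries by combination of treatments are optional.

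Protocol 3.3 decides who is in that subset: "Two consecutive morning voids prior to the Week 16 visit will be used to determine response for subsequent study treatment". Subjects whose averaged UPCR has fallen by at least 35% from Day 1 keep their drug. The rest "will switch study treatment for 16 weeks in a blinded fashion". At Week 32 a further step follows: stayers who no longer meet 35% "will be allowed to continue whichever treatment led to the greatest reduction in urinary protein excretion", or may receive either drug at the investigator's discretion. Both arms are active.

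The visible SAP neither repeats nor withdraws the non-switcher summary. SAP 3.2 groups FAS analyses by initial randomized arm, and SAP 6.2.2 gives changes from baseline by visit. The exploratory analysis text is redacted in both documents.

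**The concern.** Anyone still taking the randomized drug after Week 16 is a Week 16 responder by rule. Some pass the rule by chance, because the Day 1 reading was high or the pre-Week 16 reading was low. Later changes are still measured from Day 1, so the part of the selection that comes from a high Day 1 level persists. The part that comes from a low Week 16 reading fades.

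The resulting by-arm figure mixes drug effect with selection, and the visible text gives no warning of this. With no placebo arm, a reader cannot separate the two. At stake is the reading of long-term benefit: a table headed by drug name and running to Week 52 invites the conclusion that the effect lasts.

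**Working it through.** **Inputs from the documents.** Cut: 35% reduction in UPCR (Protocol 3.3). Protocol 8.9 assumes "a standard deviation of 50% and a 2-sided 0.05 significance level", with 16 subjects per arm and a 35% target reduction.

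**The plan's own figure.** One-sample z test within an arm: power = Φ(35/(50/√16) − 1.96) = Φ(0.84) = 80.0%. The stated 80% is reproduced. The 50% is thus the SD of percent change within one arm, and the comparison is with baseline.

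**Assumptions not in the documents.** No drug effect; log change is normal; ρ is the correlation between the log change used for selection (morning-void UPCR, Week 16) and the log change being reported (24-hour protein, Week 16 or 32).

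**Formulas.** Let the log change have mean μ and SD s, and let k = (ln 0.65 − μ)/s, where ln 0.65 = −0.431.
- Share selected = Φ(k).
- Mean change among those selected = exp(μ + s²/2) × Φ(k − ρs)/Φ(k) − 1.

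Two settings give an SD of percent change of 50%:
- A, median change 0: μ = 0, s = 0.434, k = −0.993, share Φ(k) = 16.0% (2.6 of 16).
- B, mean change 0: μ = −0.112, s = 0.472, k = −0.676, share Φ(k) = 25.0% (4.0 of 16).

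Example, setting A with ρ = 0.5: 1.099 × 0.1132/0.1604 − 1 = −22.5%.

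**If the two urine measures behave identically.** Week 16 has ρ = 1. For Week 32, ρ = 0.3 to 0.7 is assumed.

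| | Week 16 | Week 32, ρ 0.3 | ρ 0.5 | ρ 0.7 |
|---|---|---|---|---|
| A | -47% | -10% | -22% | -33% |
| B | -50% | -17% | -27% | -37% |

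**If 25% to 50% of the variance is specific to the sample type** (setting A):
- Week 16: ρ = 0.75 to 0.50, mean -36% to -22%.
- Week 32, no persistent drift: half of the remaining variance is shared through Day 1, so ρ = 0.375 to 0.25 and the mean is -15% to -7%.
- Week 32, with 30% of the variance as persistent drift: ρ = 0.30 + 0.45/2 = 0.525 down to 0.30 + 0.20/2 = 0.40, mean -24% to -17%.

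**Comparison.** Without selection, the mean for the same inert drug is +10% in setting A and 0% in setting B.

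**Actual enrolment.** With 9 subjects (SAP 1.3), 9 × 0.16 to 9 × 0.25 gives 1.4 to 2.2 chance responders across both arms.

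**The case against.** The strongest reply has five parts.

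1. *Separate samples.* Selection uses morning voids, whereas the main measure is a separate 24-hour collection, also taken at Day 1. This stands. It is why the lower end of the range is well below the 35% target. Protocol 6.6 is ambiguous on whether the 24-hour result also informs assignment.

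2. *Other displays may exist.* The exploratory endpoints and analyses are largely redacted, and the surviving fragment of Protocol 8.1.4 refers to visits other than Week 16. This stands. A reader might infer that the non-switcher table is the only long-term efficacy display; the documents do not allow that claim.

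3. *The SAP governs.* Protocol 8.5 refers efficacy details to the SAP, which shows no such table. This stands in part. SAP 7.6 lists only safety changes, but that does not prove the summary survives: the SAP also omits the protocol's confidence interval for the primary endpoint without listing the omission. The visible text does not settle whether the table will be produced. Nor do the SAP's by-visit summaries by initial arm cure the problem, because after Week 16 they pool stayers with subjects taking the other drug.

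4. *Not only responders.* Under Protocol 3.5.2, subjects who stop drug early may keep attending visits, and they never switch either. This stands. The protocol does not say whether they count, or how a change of drug at Week 32 is treated.

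5. *Little consequence.* The analysis is descriptive, by-subject listings cover all randomized subjects, SAP 4.1 tabulates switches, and only 9 subjects enrolled. This limits the harm. It does not make the by-arm figure interpretable, and a line built on one or two subjects is easily over-read.

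**Conclusion.** The concern holds for the efficacy part of the non-switcher summary. Followed as written, it gives a by-arm long-term figure biased towards benefit, with no comparator and no caveat.

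For an inert drug with an SD of 50% and a lognormal model, 16% to 25% of subjects are selected by chance. Their mean change is about -22% to -50% at Week 16 and about -7% to -37% at Week 32. The direction follows from the switching rule. The size rests on correlations that the documents do not give.

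A reader might infer that an inert drug would always show a large and lasting fall, close to the 35% target. The documents do not support that. At Week 32 the figure comes near 35% only if the two urine measures agree almost perfectly and changes persist strongly. A reader might also carry the bias over to the primary endpoint. That would be wrong: it is measured before any switch, in all FAS subjects.

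**What to change.** Change the efficacy part only, in Protocol Section 8, the synopsis and SAP 6.2.2. The Section 8 sentence covers safety data as well, so deleting it outright would lose the non-switcher safety summary, which should stay.

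1. Show post-Week 16 results by visit and randomized arm, with stayed and switched subjects side by side.
2. Report durability as the number still on the randomized drug with a reduction of at least 35% from Day 1 at Week 32 and at Week 52, over all FAS subjects in the arm. Switchers and dropouts count as not meeting it. State which urine measure is used.
3. Define non-switcher for subjects who stop drug before Week 16 and for those who change drug at Week 32.
4. Title any retained non-switcher efficacy table 'Week 16 responders only; not evidence of durable effect'.

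The cost is wording, one extra table and a less favourable long-term figure. The durability count is not free of chance either, because there is no placebo arm. In the same inert-drug model, with identical measures and ρ = 0.3 to 0.7, about 5% to 15% of all subjects would still meet 35% at both Week 16 and Week 32.

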8.1. Analysis Objectives and Endpoints

8.1.1. Analysis Objectives

The primary objective is:

- To evaluate the efficacy of filgotinib and GS-9876 in subjects with LMN

The secondary objectives are:

- To evaluate the safety and tolerability of filgotinib and GS-9876 in subjects with LMN
- To evaluate the PK of filgotinib and GS-9876 in subjects with LMN

The exploratory objectives are:

■ [REDACTED]

■ [REDACTED]

8.1.2. Primary Endpoint

[figure not shown]
The primary endpoint is the percent change in urine protein from Baseline (Day 1) to Week 16. Urine protein is assessed by urinary protein excretion during a 24-hour urine collection.

8.1.3. Secondary Endpoints

- Change from Baseline (Day 1) in urine protein (assessed by urine protein excretion during a 24-hour urine collection) at Week 16
- Change from Baseline (Day 1) in eGFR at Week 16
- Change from Baseline (Day 1) in UPCR (assessed by urine protein excretion during a 24-hour urine collection) at Week 16

- Proportion of subjects with partial remission (defined as urine protein excretion below < 3 g/d and urine protein excretion decrease by $\geq 50\%$ among subjects with Baseline (Day 1) nephrotic range proteinuria [urine protein excretion ≥ 3 g/d]; or urine protein excretion decrease by $\geq 50\%$ among subjects with subnephrotic range proteinuria [urine protein excretion < 3 g/d]) at Week 16
- Proportion of subjects with complete remission (defined as urine protein excretion below 0.5 g/day, with no hematuria) at Week 16

8.1.4. Exploratory Endpoints

[REDACTED]

[REDACTED] protein excretion below 0.5 g/day, with no hematuria) at each visit other than Week 16

8.1.5. Biomarker Endpoints

- Change in JAK-STAT-, SYK-, and disease-related biomarkers in peripheral blood and urine
- Association of changes in peripheral blood and urine biomarkers with clinical outcomes
- Association of Baseline markers with disease severity and response to filgotinib and GS-9876

8.2. Analysis Conventions

8.2.1. Analysis Sets

8.2.1.1. All Randomized

The all randomized analysis set includes all subjects who are randomized in the study. This is the primary analysis set for by-subject listings.

8.2.1.2. Efficacy

The primary analysis set for efficacy analyses will be the Full Analysis Set (FAS), which includes all randomized subjects who received at least one dose of study drug.

8.2.1.3. Safety

The primary analysis set for safety analyses will be the Safety Analysis Set, which includes all subjects who received at least one dose of study drug. All data collected during treatment plus 30 days after the last dose of study drug will be included in the safety summaries.

8.2.1.4. Pharmacokinetics

The primary analysis set for PK analyses will be the PK analysis set, which includes all subjects in the Safety Analysis Set who have at least 1 non-missing PK concentration data for GS-9876, filgotinib or their metabolites.

8.2.1.5. Biomarkers

The primary analysis set for biomarker analyses will be the Biomarker Analysis Set, which includes all subjects in the Safety Analysis Set who have at least one evaluable measurement available at any time point for a given biomarker of interest.

8.3. Data Handling Conventions

Pharmacokinetic concentration values and PK parameter values below the limit of quantitation (BLQ) will be presented as “BLQ” in the data listings. BLQ values that occur prior to the first dose will be treated as 0, BLQ values at all other time points will be treated as 1/2 of the lower limit of quantitation (LLOQ).

Laboratory data that are continuous in nature but are less than the lower limit of quantitation or above the upper limit of quantitation will be imputed to the value of the lower or upper limit minus or plus one significant digit, respectively (eg, if the result of a continuous laboratory test is < 20, a value of 19 will be assigned; if the result of a continuous laboratory test is < 20.0, a value of 19.9 will be assigned).

8.4. Demographic Data and Baseline Characteristics

Demographic and baseline measurements will be summarized using standard descriptive statistics including sample size, mean, SD, median, Q1, Q3, minimum, and maximum for continuous variables and number and percentages of subjects for categorical variables.

Demographic summaries will include sex, race/ethnicity, and age.

Baseline characteristics will include and not limited to a range of proteinuria (< 3g/d, >= 3g/d), histologic diagnosis, prior and current treatment for lupus membranous nephropathy, and patient-reported and physician-reported outcome assessments.

8.5. Efficacy Analysis

Details of the efficacy analyses will be described in the Statistical Analysis Plan (SAP).

8.5.1. Primary Analysis

The primary endpoint, the percent change from Baseline (Day 1) in 24-hour proteinuria at Week 16, will be calculated and the 95% confidence interval will be constructed for each treatment group.

8.5.2. Secondary Analyses

All continuous secondary endpoints will be summarized using an 8-number summary (n, mean, standard deviation [SD], median, 1st quartile [Q1], 3rd quartile [Q3], minimum, maximum) by treatment group. All categorical secondary endpoints will be summarized by the number and percentage of subjects who meet the endpoint definition. The 95% CI will be provided, as appropriate.

8.5.3. Exploratory Analyses

CCI

8.6. Safety Analysis

All safety analyses will be performed using the safety analysis set. Safety will be evaluated by the assessment of clinical laboratory tests, physical examinations, vital signs measurements at various time points during the study, and by the documentation of AEs.

All safety data collected on or after the date that study drug was first dispensed up to the date of last dose of study drug + 30 days will be included in the safety analysis.

8.6.1. Extent of Exposure

A subject's extent of exposure to study drug will be generated from the study drug administration page of the eCRF.

Duration of exposure to study drug will be summarized as the number of weeks between the first and last dose of the study drug, inclusive, regardless of temporary interruptions in study drug administration.

8.6.2. Adverse Events

Clinical and laboratory AEs will be coded using the Medical Dictionary for Regulatory Activities (MedDRA). System Organ Class (SOC), High-Level Group Term (HLGT), High-Level Term (HLT), Preferred Term (PT), and Lower-Level Term (LLT) will be attached to the clinical database.

Treatment-emergent adverse events (TEAEs) are defined as one or both of the following:

- Any AEs with an onset date on or after the study drug start date and no later than 30 days after permanent discontinuation of study drug.
- Any AEs leading to premature discontinuation of study drug.

Summaries (number and percentage of subjects) of treatment-emergent adverse events (by SOC, and PT) will be provided. TEAEs will also be summarized by relationship to study drug and severity.

All observed AEs will be presented in by-subject listings.

